Appendix H. DATA MANAGEMENT AND RECORD KEEPING

Direct Access to Source Data and Documents

All patient data must have supportive original source documentation in the medical records, or equivalent, before they are transcribed to the case report form (CRF). Data may not be recorded directly on the CRF and considered as source data unless the sponsor provides written instructions specifying which data are permitted to be recorded directly to the CRF.

If data are processed from other institutions or by other means (eg, clinical laboratory, central image center, or electronic diary data) the results will be sent to the investigational center, where they will be retained but not transcribed to the CRF, unless otherwise noted in the protocol. These data may also be sent electronically to the sponsor (or organization performing data management).

The medical experts, study monitors, auditors, Independent Ethics Committee (IEC)/Institutional Review Board (IRB), and inspectors from competent authority (or their agents) will be given direct access to source data and documents (eg, medical charts/records, laboratory test results, printouts, videotapes) for source data verification, provided that patient confidentiality is maintained in accordance with national and local requirements.

The investigator must maintain the original records (ie, source documents) of each patient's data at all times. The investigator must maintain a confidential patient identification list that allows the unambiguous identification of each patient.

Data Collection

Data will be collected using CRFs that are specifically designed for this study. The data collected on the CRFs will be captured in a clinical data management system (CDMS) that meets the technical requirements described in Title 21 Code of Federal Regulation Part 11 (United States of America) and documents of other concerned competent authorities. Before using the CDMS, it will be fully validated and all users will receive training on the system and study-specific training. After they are trained, users will be provided with individual system access rights.

Data will be collected at the investigational center by appropriately designated and trained personnel, and CRFs must be completed for each patient who provided informed consent. Patient identity should not be discernible from the data provided on the CRF.

If data are processed from other sources (eg, central laboratory, bioanalytical laboratory, central image center, electronic diary data, or electronic patient-reported outcome tablet), these data will be sent to the investigational center, where they will be retained but not transcribed to the CRF, unless otherwise noted in the protocol. These data may also be sent electronically to the sponsor (or organization performing data management). All patient data must have supportive original source documentation in the medical records, or equivalent, before they are transcribed to the CRF. Data may not be recorded directly on the CRF and considered as source data unless the sponsor provides written instructions specifying which data are permitted to be recorded directly to the CRF.

For patients who enter a study but do not meet entry criteria, at a minimum, data for screening failure reason, demography, and adverse events from the time of informed consent will be entered in the CRF.

Data Quality Control

Data Management is responsible for the accuracy, quality, completeness, and internal consistency of the data from this study. Oversight will be carried out as described in the sponsor's Standard Operating Procedures (SOPs) for clinical studies. Day-to-day data management tasks for this study are delegated to a contract organization, and these functions may be carried out as described in the SOPs for clinical studies at that organization. These SOPs will be reviewed by the sponsor before the start of data management activities.

Data will be verified by the study monitor using the data source, and reviewed by Data Management using both automated logical checks and manual review. Data identified as erroneous, or data that are missing, will be referred to the investigational center for resolution through data queries. Any necessary changes will be made in the clinical database, and data review and validation procedures will be repeated as needed. Data from external sources will be compared with the information available in the CDMS, and any discrepancies will be queried.

Applicable terms will be coded according to the coding conventions for this study.

At the conclusion of the study, the CDMS and all other study data will be locked to further additions or corrections. Locking the study data represents the acknowledgement that all data have been captured and confirmed as accurate. All data collected will be approved by the investigator at the investigational center. This approval acknowledges the investigator's review and acceptance of the data as being complete and accurate.

Archiving of Case Report Forms and Source Documents

Sponsor Responsibilities

The original CRFs will be archived by the sponsor. Investigational center-specific CRFs will be provided to the respective investigational centers for archiving.

Investigator Responsibilities

The investigator must maintain all written and electronic records, accounts, notes, reports, and data related to the study and any additional records required to be maintained under country, state/province, or national and local laws, including, but not limited to:

- full case histories
- signed informed consent forms
- patient identification lists
- CRFs for each patient on a per-visit basis
- data from other sources (eg, central laboratory, bioanalytical laboratory, central image center, electronic diary)
- safety reports
- financial disclosure reports/forms

- reports of receipt, use, and disposition of the IMPs
- copies of all correspondence with sponsor, the IEC/IRB, and any competent authority

The investigator will retain all records related to the study and any additional records required, as indicated by the protocol and according to applicable laws and regulations, until the contract research organization or sponsor notifies the institution in writing that records may be destroyed. If, after 25 years from study completion, or earlier in the case of the investigational center closing or going out of business, the investigator reasonably determines that study record retention has become unduly burdensome, and sponsor has not provided written notification of destruction, then the investigator may submit a written request to sponsor at least 60 days before any planned disposition of study records. After receipt of such request, the sponsor may make arrangements for appropriate archival or disposition, including requiring that the investigator deliver such records to the sponsor. The investigator shall notify the sponsor of any accidental loss or destruction of study records.

APPENDIX I. PUBLICATION POLICY

All unpublished information given to the investigator by the sponsor shall not be published or disclosed to a third party without the prior written consent of the sponsor.

The results of this study may be published or presented at scientific meetings. If this is foreseen, the investigator agrees to submit all manuscripts or abstracts to the sponsor before submission. This allows the sponsor to protect proprietary information and to provide comments.

The sponsor will comply with the requirements for publication of study results:

“Recommendations for the Conduct, Reporting, Editing, and Publication of Scholarly Work in Medical Journals” (www.ICMJE.org). Publication of the results will occur in a timely manner according to applicable regulations. In accordance with standard editorial and ethical practice, the sponsor will generally support publication of multicenter studies only in their entirety and not as individual investigational center data. In this case, a coordinating investigator will be designated by mutual agreement.

Authorship will be determined by mutual agreement and in line with the following International Committee of Medical Journal Editors authorship requirements:

- substantial contributions to the conception or design of the work; or the acquisition, analysis, or interpretation of data for the work
- drafting the work or revising it critically for important intellectual content
- final approval of the version to be published
- agreement to be accountable for all aspects of the work in ensuring that questions related to the accuracy or integrity of any part of the work are appropriately investigated and resolved

The publications committee established by the sponsor will oversee this process. Additional publications may follow. Policies regarding the publication of the study results are defined in the financial agreement.

No patent applications based on the results of the study may be made by the investigator nor may assistance be given to any third party to make such an application without the written authorization of the sponsor.

Appendix J. LIST OF EXAMPLES OF OPPORTUNISTIC INFECTIONS

- Bacterial enteric infections
- Bartonellosis
- Candidiasis (excluding vulvovaginal candidiasis)
- Chagas disease
- Coccidioidomycosis
- Community-acquired pneumonia
- Cryptococcosis
- Cryptosporidiosis
- Cystoisosporiasis (Formerly Isosporiasis)
- Cytomegalovirus Disease
- Hepatitis B Virus Infection
- Hepatitis C Virus Infection
- Herpes Simplex Virus
- Histoplasmosis
- Human Herpesvirus-8
- Human Papillomavirus
- Leishmaniasis
- Malaria
- Microsporidiosis
- *Mycobacterium avium*
- *Mycobacterium tuberculosis*
- *Pneumocystis Pneumonia*
- Progressive Multifocal Leukoencephalopathy/JC Virus Infection
- Syphilis
- Talaromycosis (Formerly Penicilliosis)
- *Toxoplasma gondii*
- Varicella-Zoster Virus

Any suspected opportunistic infections (ie, infections that are not listed above [eg, *Clostridium difficile*, aspergillosis, etc] and/or infections that occur more frequently and are more severe than expected) are to be reported.

Further details are available in “Guidelines for Prevention and Treatment of Opportunistic Infections in HIV-Infected Adults and Adolescents.” Available at: <https://aidsinfo.nih.gov/guidelines/html/4/adult-and-adolescent-opportunistic-infection/0>). Accessed 18 August 2021. Vulvovaginal candidiasis was removed from the list above as it may be expected in the study patient population.

APPENDIX K. LIVER SAFETY: REQUIRED ACTIONS AND FOLLOW-UP ASSESSMENTS GUIDELINES

The liver chemistry stopping and increased monitoring criteria (see Section 4.4.1) have been designed to assure patient safety and evaluate liver event etiology and require follow up assessments as detailed below:

Required Actions and Follow up Assessments	
Actions	Follow up Assessment

 ○ Withhold study drug. ○ Report the event to Sponsor within 24 hours ○ Complete the liver event CRF and complete an SAE/PDAESI form. ○ Perform liver chemistry event follow-up assessments. ○ Monitor the patient and repeat liver chemistries (include ALT, AST, alkaline phosphatase, bilirubin and INR) weekly (if bilirubin >2x ULN or INR>1.5, twice weekly) until liver chemistries resolve, stabilize or return to within baseline ○ Do not restart/patient with study drug unless allowed per protocol and Sponsor approval is granted. ○ If restart is not allowed per protocol or not granted, permanently discontinue study treatment and complete the assessments for the early termination visit and the follow-up period in the study. 	
 ○ Viral hepatitis serology¹ ○ Obtain INR. ○ Obtain blood sample for pharmacokinetic analysis, as soon as possible, and at least within 7 days. ○ Obtain complete blood count with differential to assess eosinophilia. ○ Record the appearance or worsening of clinical symptoms of liver injury, or hypersensitivity, on the AE report form. ○ Record use of concomitant medications on the concomitant medications report form including acetaminophen, herbal remedies, other over the counter medications. ○ Record alcohol use on the liver event CRF ○ If bilirubin and/or INR are elevated: 
 ■ Test Anti-nuclear antibody, anti-smooth muscle antibody, Type 1 anti-live kidney microsomal antibodies, and quantitative total immunoglobulin G (IgG) or gamma globulins. ■ Check serum acetaminophen levels if definite or likely acetaminophen use in the preceding week: ■ Liver imaging (ultrasound, magnetic resonance, or computerized tomography) and/or liver biopsy. ■ Consider a specialist or hepatology consultation.

¹Includes: Hepatitis A immunoglobulin M (IgM) antibody; HBsAg and HBcAb; Hepatitis C RNA; Cytomegalovirus IgM antibody; Epstein-Barr viral capsid antigen IgM antibody (or if unavailable, obtain heterophile antibody or monospot testing); Hepatitis E IgM antibody.

APPENDIX L. OPERATING CHARACTERISTICS AND ASSUMPTIONS FOR FINAL AND INTERIM ANALYSIS

Final Analysis and Interim Futility Analysis

A Beta-binomial model with a non-informative Beta (1,1) prior will be used to analyze the primary response endpoint, clinical remission (for UC) or endoscopic response (for CD), hereafter denoted as “response”. The model will be fit separately for each dose within each indication.

Assumptions:

Various scenarios for remission (UC), response rates (CD) are assumed as outlined in [Table 9](#) to investigate the operating characteristics.

Table 9: Remission (UC), Response (CD) Rates Scenarios for Clinical Trial Simulations

Scenario	Indication	Placebo (%)	Low Dose 450 mg Q2W (%)	High Dose 900 mg Q2W (%)
Null	UC	8	8	8
	CD	12	12	12
Intermediate Efficacy	UC	8	20	20
	CD	12	25	25
Efficacy	UC	8	30	30
	CD	12	34	34
Efficacy-high dose only	UC	8	8	30
	CD	12	12	34

CD=Crohn's disease; Q2W=every 2 weeks; UC=ulcerative colitis.

Number of Patients at the Interim Analysis:

The interim analysis for each indication is planned when approximately 50% of patients in the indication have completed the 14-week primary efficacy readout or had the opportunity to do so. Operating characteristics were obtained from simulations assuming that exactly 20 patients per arm in the corresponding indication will be included in the interim analysis. Since the analysis is separate for each indication, no assumptions on the expected difference in recruitment rate between UC and CD are required.

Statistical Decision Criteria – Final Analysis:

A TEV-48574 dose will be declared successful at the final analysis if the posterior probability that the response rate in the TEV-48574 dose is higher than the response rate in the placebo arm is ≥ 0.90 , ie, the success criterion for each dose within indication is:

- Posterior Probability (TEV-48574 response rate – placebo response rate >0) ≥ 0.90

Statistical Futility Cutoff – Interim Analysis:

The same Bayesian Beta-Binomial model described in the primary analysis model will be used for the interim futility analysis for each dose within each indication. A TEV-48574 dose will be declared futile at the interim analysis if the posterior probability that the response rate in the TEV-48574 dose is higher than the response rate in the placebo arm is <0.30 , ie, the futility criterion for each dose within indication is:

- Posterior Probability (TEV-48574 response rate – placebo response rate >0) <0.30

Operating Characteristics:

Clinical trial simulations were performed under the assumptions for the interim and primary analysis to generate the operating characteristics (presented in [Table 10](#)), for a target sample size of 40 patients per arm in each indication, and an interim analysis for futility for each indication at 21 patients per arm in the indication. The posterior probability futility cutoff is <0.30 for each indication and final success posterior probability cutoff is ≥ 0.90 .

Table 10: Operating Characteristics for Interim and Final Analysis – All Scenarios

	UC						CD					
	% F futile at interim analysis			% Success at end of trial			% F futile at interim analysis			% Success at end of trial		
	TEV-48574 doses											
	450 mg Q2W	900 mg Q2W	Both Doses	450 mg Q2W	900 mg Q2W	At least 1 dose	450 mg Q2W	900 mg Q2W	Both Doses	450 mg Q2W	900 mg Q2W	At least 1 dose
Null	25%	24%	11%	8%	8%	13%	24%	24%	12%	9%	10%	16%
Intermediate efficacy both doses	4%	4%	1%	61%	61%	77%	4%	4%	1%	59%	59%	76%
Efficacy both doses	1%	1%	<1%	91%	91%	98%	1%	1%	<1%	87%	87%	95%
Efficacy high dose only	24%	1%	<1%	8%	91%	91%	25%	1%	1%	10%	87%	87%

CD=Crohn's disease; Q2W=every 2 weeks; UC=ulcerative colitis.

Note: Beta-Binomial model with non-informative prior; posterior probability futility cutoff: <0.30 ; final analysis posterior probability cutoff of ≥ 0.90 .

Note: Operating characteristics based on 500,000 simulations.

These simulations demonstrate that the probability of a false positive result is $\leq 16\%$ for each indication, while the probability of declaring success for at least 1 dose within each indication under the efficacy assumption for both doses is $\geq 95\%$.

The futility threshold was selected to control the probability to declare an effective dose to be futile at a maximum of 1%, while making the correct decision in the null with a probability of approximately 25%.

Since the analysis is done separately for each dose and each indication, the probability to demonstrate efficacy in one dose is not affected by the other dose. Moreover, no inflation of the Type 1 error rate is expected in hypothetical discordant scenarios where TEV-48574 is effective in 1 indication but not in the other.

Safety Stopping Rules

- For each of the 4 types of AEs listed below (Table 11), a Bayesian analysis using the Beta-binomial model with a non-informative Beta(1,1) prior will be conducted. The posterior probability of each type of AE will be compared for each dose and the 3 dose levels combined versus placebo. If the posterior probability that the AE rate in the active group is larger than the AE rate in the placebo group with a posterior probability cutoff defined below, the stopping rule will be triggered. The analyses and evaluation will be conducted for UC and CD separately and across the entire study population.

Table 11: Posterior Probability of Adverse Events

AE type	Posterior probability cutoff
Serious adverse events (aggregated)	90%
CTCAE grade 3/4 adverse events (aggregated)	90%
Opportunistic and severe and/or serious infections	85%
Anaphylaxis	85%

AE=adverse event; CTCAE= Common Terminology Criteria for Adverse Events.

- The DMC will review in detail any safety signal that meets the safety stopping rule, and take into account the totality of safety data. Additional analyses, eg, SAEs in the same HLT, may be performed.
- The DMC will make a recommendation if the safety signal and the totality of the safety data warrants stopping the dose/indication/study.

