8.1. Adverse Events and Adverse Device Effects

8.1.1. Definition of an Adverse Event

An adverse event is any untoward medical occurrence in a patient or clinical investigation patient administered a pharmaceutical product and which does not necessarily have to have a causal relationship with this treatment.

An adverse event can, therefore, be any unfavorable and unintended physical sign, symptom, or laboratory parameter that develops or worsens in severity during the course of this study, or significant worsening of the disease under study, or of any concurrent disease, whether or not considered related to TEV-48574.

Accordingly, an adverse event can include any of the following:

- a new condition or the worsening of a pre-existing condition
- intercurrent illnesses
- physical injuries and the mechanism that caused the injury
- events possibly related to concomitant medication
- drug or drug/device or device/device interactions
- events occurring during diagnostic procedures or during any washout phase of this study
- laboratory or diagnostic test abnormalities

(Note: Abnormal laboratory or diagnostic test results at the screening visit that preclude a patient from entering the study or receiving study treatment are not considered adverse events.)

IBD manifestations are efficacy variables for this study and should be captured on the relevant specific CRF; accordingly, these events should not be recorded as adverse events unless assessed as more severe than the patient's usual disease course. Extraintestinal manifestations of the patient's disease (eg, arthralgias, arthritis, or uveitis) that develop or worsen during the study should be reported as adverse events. IBD manifestations that are more severe than the patient's usual course of disease and meet the criteria for a serious adverse event (eg, required hospitalization) should be reported as a serious adverse event.

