10.1. Sample Size and Power Considerations

A total study sample size of 240 patients is planned, with 120 patients (40 patients per dose arm) each for the 2 indications of UC and CD.

The sample size does not include patients that were randomized to the 1800 mg treatment group prior to Amendment 03 with Revision 01.

Assumptions:

The clinical remission and endoscopic response rates assumed in the sample size and related operating characteristics computations are as follows:

- Clinical remission rates in UC indication: 8% for placebo; 30% for TEV-48574 low- and high-dose groups, respectively
- Endoscopic response rates in CD indication: 12% for placebo; 34% for TEV-48574 low- and high-dose groups, respectively

Simulation-based operating characteristics for the analysis of the primary efficacy variable using a Bayesian Beta Binomial model are presented in [Table 8](#). This model uses a posterior probability cutoff of <0.30 for the assessment of futility at the interim analysis and a posterior probability cutoff of ≥ 0.90 to declare success at the final analysis.

For UC, the family-wise false-positive rate (ie, probability of making at least 1 false-positive conclusion under the null assumption for both doses) is 13%, and the probability of declaring success for at least 1 dose group is 98%, under the assumptions above.

For CD, the family-wise false-positive rate is 16%, and the probability of declaring success for at least 1 dose is 95%, under the assumptions above.

Table 8: Operating Characteristics of Interim and Final Analysis

	UC						CD					
	% F futile at interim analysis			% Success at end of trial			% F futile at interim analysis			% Success at end of trial		
	TEV-48574 doses											
	450 mg Q2W	900 mg Q2W	Both Doses	450 mg Q2W	900 mg Q2W	At least 1 dose	450 mg Q2W	900 mg Q2W	Both Doses	450 mg Q2W	900 mg Q2W	At least 1 dose
Null	25%	24%	11%	8%	8%	13%	24%	24%	12%	9%	10%	16%

	UC						CD					
	% F futile at interim analysis			% S successful at end of trial			% F futile at interim analysis			% S successful at end of trial		
	TEV-48574 doses											
	450 mg Q2W	900 mg Q2W	Both Doses	450 mg Q2W	900 mg Q2W	At least 1 dose	450 mg Q2W	900 mg Q2W	Both Doses	450 mg Q2W	900 mg Q2W	At least 1 dose
Intermediate efficacy both doses	4%	4%	1%	61%	61%	77%	4%	4%	1%	59%	59%	76%
Efficacy both doses	1%	1%	<1%	91%	91%	98%	1%	1%	<1%	87%	87%	95%

CD=Crohn's disease; Q2W=every 2 weeks; UC=ulcerative colitis.

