10.13. Planned Interim Analysis

Interim analyses for safety and efficacy are planned for this study. An interim efficacy/futility analysis is planned in each indication (UC and CD) when approximately 50% of patients in the indication have completed the 14-week primary efficacy readout time point or had the opportunity to do so. This is expected to yield approximately 20 evaluable patients per treatment group for each indication in the interim analysis.

Due to study recruitment acceleration or other operational considerations, the interim analysis for efficacy/futility will not be conducted as it will be impractical and have limited utility.

In the interim analysis, the same Bayesian Beta-Binomial model described in the primary analysis model will be used to analyze the primary efficacy response variable for each dose within each indication. The futility criterion for each dose is:

- Posterior probability (TEV-48574 response rate – placebo response rate >0) <0.30

Refer to Table 10 and Appendix L for operating characteristics of the interim and final analysis.

In addition to futility, efficacy criteria, which is nonbinding, will be incorporated for the purpose of internal decision making for further development planning. Details of the efficacy criteria will be provided in the Statistical Analysis Plan.

Additionally periodic analysis of safety data will be done during the study. Analyses will focus on the following events:

- Incidence of serious adverse events
- Incidence of CTCAE grade 3 or grade 4 events
- Incidence of opportunistic infections and severe and/or serious infections
- Incidence of anaphylaxis

A Bayesian continuous monitoring approach will be employed for the above events, looking at the posterior probability for the incidence being greater on active treatment relative to placebo. A posterior probability exceeding 0.85 to 0.9 will trigger consideration for stopping the study or individual dose arms within the study.

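### The two aggregated safety triggers count worsening of the patients' own UC or CD, which can dilute a toxicity excess; the IDMC should also see both comparisons without it

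*Protocol*

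**What the plan says.** Appendix L (Safety Stopping Rules, Table 11) names four event types. The two broadest are "Serious adverse events (aggregated" and "CTCAE grade 3/4 adverse events (aggregated", each with a 90% cutoff. Infections and anaphylaxis have their own 85% cutoffs. For each type, "a Bayesian analysis using the Beta-binomial model with a non-informative Beta(1,1) prior will be conducted", with every dose and the pooled doses set against placebo. "The analyses and evaluation will be conducted for UC and CD separately and across the entire study population". Section 10.13 describes the same monitoring as "looking at the posterior probability for the incidence being greater on active treatment relative to placebo" and says that crossing the cutoff leads to consideration of stopping. Neither place removes, or counts separately, events that are worsening of the patient's own UC or CD.

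Section 8.1.1 classes IBD manifestations as efficacy variables and keeps them out of AE recording unless they are worse than the patient's usual course. Those that exceed the usual course "of disease and meet the criteria for a serious adverse event (eg, required hospitalization) should be reported as a serious adverse event". They then enter both the SAE count and, when graded 3 or 4, the grade 3/4 count.

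Appendix L provides for detailed DMC review, with possible further analyses such as SAEs within one high-level term, for a signal that has met the rule.

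**The concern.** The same event can count as loss of efficacy under section 8.1.1 and as toxicity under Table 11. The planning assumptions in section 10.1 (8% v 30% remission in UC, 12% v 34% endoscopic response in CD) imply less active disease on an effective dose. If serious flares follow that pattern, placebo carries more of them, and they offset toxic events on the active arm in an all-event comparison. Even flares that are equal between arms add noise and lower the chance of detecting a given excess.

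The detailed review in Appendix L starts from a signal that meets the rule, so a diluted signal does not prompt it. Section 10.13 also states that the efficacy/futility interim analysis will not be conducted, so no scheduled efficacy display would help the IDMC see that placebo flares lie behind a balanced SAE total.

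**Working it through.** **Formula.** With x events in n patients and a Beta(1,1) prior, each arm's rate has posterior Beta(1+x, 1+n−x). The rule computes P(p_active > p_placebo) from two independent posteriors; here it fires at 0.90 or above.

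**Check against the plan's own figures.** The safety rule has no stated operating characteristics, but Table 10 uses the same model and cutoff at 40 per arm. The calculation reproduces it:
- per dose, null/efficacy: UC 7.8%/90.9% (stated 8%/91%); CD 9.5%/87.0% (stated 9–10%/87%)
- at least one dose, null: UC 13.5% (13%), CD 16.0% (16%)
- at least one dose, efficacy: UC 97.5% (98%), CD 95.4% (95%).

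**Sample sizes.** Section 10.1 plans the trial "with 120 patients (40 patients per dose arm) each for the 2 indications of UC and CD". One dose against placebo is therefore 40 v 40 within an indication and 80 v 80 across both.

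**Count example, 40 v 40.** Non-flare SAEs of 4 v 0 give a posterior of 0.973, so the rule fires. Adding flare SAEs of 1 v 4 makes 5 v 4: posterior 0.631, and it does not fire. The result depends on the split. With one placebo flare (5 v 1) the posterior is 0.946 and the rule still fires; with two (5 v 2) it is 0.868 and it does not.

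**Chance of firing at one look.** Sum Bin(x_a; n, p_a) × Bin(x_p; n, p_p) over all pairs (x_a, x_p) with posterior at least 0.90. All rates are assumptions: non-flare SAEs 8% active v 2% placebo, with flare rates added to these.

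| Flares, active v placebo | All SAEs, active v placebo | n = 40 | n = 80 |
|---|---|---|---|
| excluded | 8% v 2% | 37% | 66% |
| 2% v 4% | 10% v 6% | 22% | 35% |
| 2% v 6% | 10% v 8% | 14% | 19% |
| 2% v 8% | 10% v 10% | 9% | 9.5% |
| 5% v 5% | 13% v 7% | 33% | 48% |

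In the 2% v 8% row the total rates are equal, so 9% and 9.5% are simply the rule's false-alert rates.

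**A second set of assumed rates.** Toxicity SAEs 10% v 2%, with flare rate d and toxicity rate t combined as 1 − (1−d)(1−t). At 80 v 80 the chance of firing is 81% with flares excluded. With placebo v active flares of 5% v 2%, 8% v 3%, 10% v 3% and 15% v 5% it is 40%, 23%, 13% and 5%. With equal 5% flares it is 60%. More patients do not cure a bias in the compared rates: at 15% v 5% the chance is 6%, 5% and 4% for 40 v 40, 80 v 80 and 160 v 80.

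**False alerts from an added comparison.** With no toxicity (non-flare SAEs 2% in each arm), the flare-excluded comparison fires in 2.1% (n = 40) and 5.2% (n = 80) of single looks. The all-event comparison with equal 5% flares fires in 7.2% and 9.0%.

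**The case against.** The strongest reply is that nothing here is inconsistent: section 8.1.1 says when IBD worsening becomes an AE, and Appendix L counts AEs. An all-cause screen is a defensible, deliberately broad choice. Section 10.13 leaves statistical methods to the SAP, and sections 6.9.3 and 10.13 leave stopping details and decision criteria to the IDMC charter; an exclusion list could sit in either. This stands in part. But Appendix L itself fixes the event categories, model, prior and cutoffs, and the dilution follows from what it fixes.

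The second reply is that a silent trigger is not a clean safety review. This stands. The trigger only prompts consideration. Under section 6.9.3 the IDMC, with two IBD clinicians, reviews unblinded safety data periodically whether or not a trigger fires. Flares do not affect the infection and anaphylaxis triggers as such, and section 4.4.2 lets the sponsor stop for any relevant toxicity. A reader might infer that an effective but toxic dose would pass unnoticed; the documents do not support that.

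The third reply is that the size is assumed, and this stands fully. Remission and endoscopic response rates say nothing direct about serious flares, and only worsening beyond the usual course is counted. An excess on placebo is an inference from the assumed efficacy. At 40 per arm with equal flares the loss is small (37% to 33%).

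Two further readings should be resisted. One is that an ineffective dose would set off the rule through flares: with equal flare rates, firing is chance, at the 7.2% and 9.0% shown above. The other is that disease worsening should be taken out of the triggers. That would remove the formal prompt for drug-induced bowel worsening, which is a harm the IDMC needs to see.

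**Conclusion.** The point holds as a dilution of two of the four triggers. The aggregated SAE and grade 3/4 comparisons mix disease worsening with toxicity. If the drug reduces serious flares, the mix lowers the chance that a true excess prompts the detailed review. Across the first set of assumed rates the loss at one look runs from 4 percentage points (37% to 33%, equal flares, 40 per arm) to about 56 points (66% to 9.5%, placebo flares 8%, 80 per arm). These figures rest on assumed SAE and flare rates and a single look at full enrolment; repeated looks would raise the chance of firing in both versions. What the documents establish is the mechanism, and its direction if the planned efficacy carries over to serious flares. They do not establish its size, nor that safety oversight as a whole would fail. An inexpensive addition to the safety outputs is warranted; a replaced rule is not.

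**What to change.** Reconcile section 8.1.1 with section 10.13 and Appendix L by stating plainly that the two aggregated triggers include UC and CD worsening. Leave the existing triggers, model and cutoffs unchanged. At each safety review, add for the IDMC's information:
- the same Beta-binomial comparison for SAEs and for grade 3/4 events with UC/CD worsening excluded, using a MedDRA term list fixed before the next look
- a separate table of the disease-worsening events by arm, shown beside the all-event results.

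The cost is a short term list, one extra flag in the unblinded reporting team's programs, and a few lines in Appendix L and the IDMC charter. Deciding which terms are disease worsening needs judgement, which is one reason to keep the all-event comparison, and the extra comparison may give a few more false alerts.
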